Sallman *et al.* performed an internal analysis of molecularly profiled patients at Moffitt Cancer Center and also identified that the clonal burden, or variant allele frequency (VAF), had significant impact on clinical phenotype and more importantly further stratified prognosis over binary mutational analysis alone and/or clinical prognostic models²³. Specifically, MDS patients with a TP53 VAF > 40% had a median overall survival (OS) of 124 days versus an OS that was not reached in patients with VAF < 20% (hazard ratio (HR), 3.52; P = 0.01) with validation in an independent cohort (HR, 4.94, P = 0.01). Overall, TP53 mutant MDS and AML patients have a median OS ranging from 5-9 months with 8 months representing the best estimate when restricting to MDS and oligoblastic AML (20-30% blasts) (Figure 1)^{20,23,24;25,26}.

[figure not shown]

Figure 1. Historical Overall Survival for *TP53* Mutant MDS/AML ($\leq 30\%$ blasts) Treated with Frontline Azacitidine (Source: Moffitt Cancer Center Database).

Median OS of 7.6 Months in MDS/AML patients treated with frontline AZA (n=51).

Together, these data highlight the dismal outcomes of *TP53* mutant patients and the dire need for the development of novel therapeutic strategies, particularly in this patient population.

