5.0 SELECTION AND WITHDRAWAL OF SUBJECTS

Patients considered for enrollment on this study must have a diagnosis of MDS based on the WHO classification, documented *TP53* mutation, and meets IPSS-R classification of intermediate, high, or very high-risk disease. The patients must meet all inclusion and no exclusion criteria. Investigators must be listed on the FDA 1572 form in order to be authorized to obtain information consent. No study-specific procedures can be performed until the patient has signed an ICF that has been approved by the IRB or IEC. Procedures that are performed prior to patients signing ICFs can be used to satisfy protocol requirements if these procedures are performed as routine medical care for the patient's underlying disease or other illnesses.

The study will enroll patients with *TP53* mutations that are not benign or likely benign, as determined by local Next Generation Sequencing (NGS) and a study-specific variant interpretation algorithm. The *TP53* variant interpretation will be verified centrally prior to inclusion. Central NGS testing including *TP53* will subsequently be conducted on all patients after enrollment. If there is discordance between local and central testing patients will be allowed to remain on study.

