7.2.2 Randomization

Randomization will occur after screening, once a patient has had their eligibility confirmed, has agreed to participate and is ready to start on the study treatment.

Stratified randomization will be based on age group (< 65 years and ≥ 65 years). Patients will be assigned to one of two strata based on age group (< 65 years and ≥ 65 years), and then assigned to the particular treatment arm from the randomization list for that stratum. Randomization will be balanced within each stratum with patients randomly assigned with equal probability (1:1 allocation) to one of the two treatment arms (APR-246 + azacitidine or azacitidine). Permuted block randomization (random allocation within block) will be used to assign patients to treatments within each stratum.

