9.0 STATISTICS

9.1 Sample Size

This trial will include 154 patients with 77 patients randomized in a 1:1 ratio to each of the two treatment arms (APR-246 + azacitidine treatment versus azacitidine treatment alone).

If the true CR rate is 50% for the treatment arm and 25% for the control arm, the trial will have 90% power to detect a statistically significant effect in favor of the APR-246 at a 2-sided alpha = 0.05 significance level.

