9.3 Statistical Methods

9.3.1 Efficacy Analyses

Primary endpoint CR will be summarized for all randomized patients (ITT) as the proportion of patients (%) with CR. CR will be compared between treatment arms using a Cochran-Mantel-Haenszel (CMH) test stratified by age (< 65 years versus ≥ 65 years). In addition to presenting the CR rate and associated exact 95% CI for each treatment arm, the treatment effect will be described using the CMH estimate of the common odds ratio together with its associated 95% CI.

Duration of response (DOR) is defined as the time from the date when criteria for

response) are met to the date of relapse, progression, or death due to any cause, whichever occurs first. Patients alive without relapse or progression will have their DOR censored at the date of the last clinical assessment. The duration of CR will be summarized in each treatment arm by providing the median DOR together with associated 95% CI, using Kaplan-Meier methodology.

Overall response will be summarized in number (%) of patients in each category of responses (CR, PR, mCR with HI, mCR without HI, HI). ORR will be analyzed by using the similar method as primary endpoint CR. DOR, as defined above, will also be evaluated in regards to ORR.

Time to AML is calculated from first day of study treatment to first onset of AML. Kaplan-Meier methodology will be utilized. Rate of AML transformation will be analyzed by using the same method as primary endpoint CR.

Survival data are collected at treatment and follow-up periods. Patients will be followed until death. Overall Survival (OS) is defined as the number of days from the date of randomization to the date of death. Kaplan-Meier methodology will be utilized.

Relapse-free survival (RFS) is defined as the time from the date of randomization to disease relapse, progression or death from MDS, whichever occurs first. If neither event occurs, RFS will be censored at the date of the last assessment. Kaplan-Meier methodology will be utilized.

Time to AML, OS and RFS will be analyzed using the similar methods as DOR.

Transition rate to SCT will be analyzed using the similar methods as complete response rate.

Important subgroup analyses will be detailed in the Statistical Analysis Plan.

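### OS is to be summarised without baseline TP53 VAF, which Section 2.2 reports as strongly prognostic for OS; a VAF-adjusted Cox model should be pre-specified

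*Combined protocol and SAP*

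**What the plan says.** Section 9.3.1 handles three endpoints in one sentence: "Time to AML, OS and RFS will be analyzed using the similar methods as DOR". The method it points to is: "The duration of CR will be summarized in each treatment arm by providing the median DOR together with associated 95% CI, using Kaplan-Meier methodology". It names no log-rank test, Cox model, hazard ratio or covariate for OS, RFS or time to AML.

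Section 2.2 reports that patients with VAF above 40% "had a median overall survival (OS) of 124 days versus an OS that was not reached" in those below 20%, with a hazard ratio of 3.52, and 4.94 in an independent cohort (P = 0.01 for each). It adds that VAF refined prognosis beyond mutation status and clinical scores.

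Section 7.2.2: "Stratified randomization will be based on age group". No other factor is used. In Section 5.0, central NGS covering TP53 "will subsequently be conducted on all patients after enrollment". Marrow is collected at screening (Section 7.2.1), with blood accepted if no aspirate is available. In the synopsis, VAF is an exploratory measure that may be included, and Section 9.3.2 warns that some listed analyses may not be done.

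The only covariate adjustment is the transplant-related IPCW analysis in Section 8.2.3, whose baseline predictors are not named.

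**The concern.** Every enrolled patient is TP53-mutant, so mutation status cannot separate prognosis within the trial, but VAF can. The protocol presents VAF as a strong predictor of survival, neither stratifies on it nor adjusts for it, and plans sequencing that could supply it.

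In a survival comparison, omitting a strong prognostic covariate pulls the estimated hazard ratio towards 1 and lowers power, even with perfect balance between arms. With 154 patients that could matter for OS. The trial is also open-label, so a VAF adjustment added after results are known would look data-driven, whereas one fixed now is credible.

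**Working it through.** **The plan's own figure.** Section 9.1: "This trial will include 154 patients with 77 patients randomized in a 1:1 ratio"; "If the true CR rate is 50% for the treatment arm and 25% for the control arm, the trial will have 90% power", at a "2-sided alpha = 0.05 significance level".
- Pooled rate 0.375; null SE = sqrt(2 × 0.375 × 0.625 / 77) = 0.0780.
- Alternative SE = sqrt((0.25 + 0.1875) / 77) = 0.0754.
- z = (0.25 − 1.96 × 0.0780) / 0.0754 = 1.29, so power is 90.1%.

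The CR figure reproduces and is unaffected by this point. No OS figure is stated to reproduce.

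**Inputs for OS**
- From the documents: 77 per arm; control median 8 months (best estimate in Section 2.2); VAF hazard ratios 3.52 and 4.94; total duration 33 months, the middle of the 30-36 in Section 4.5.
- Assumed: 18 months' accrual; treatment hazard ratio 0.60, 0.65 or 0.70; proportional hazards; no age effect; the 20-40% VAF group at the square root of the VAF hazard ratio; VAF mixes (<20 / 20-40 / >40%) of 33/34/33, 20/30/50 and 10/20/70.
- VAF hazard ratios of 2.0 and 1.0 were added as weaker cases.

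**Method.** 1,500 simulated trials per scenario. A Cox Wald test for treatment alone was compared with one that also contained VAF group, two-sided 0.05. The Monte Carlo standard error is about 1.3 points per power figure.

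**Cross-check without a VAF effect.** Schoenfeld, 120 deaths, hazard ratio 0.65: sqrt(120/4) × |ln 0.65| − 1.96 = 5.477 × 0.431 − 1.96 = 0.40, so power is 65.5%. The simulation gives 66-67%.

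**Results.** OS power, unadjusted → adjusted; ranges cover the three mixes.

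| VAF HR | Treatment HR 0.60 | 0.65 | 0.70 |
|---|---|---|---|
| 1.0 | 79% → 79% | 66-67% → 65-67% | 49-52% → 50-52% |
| 2.0 | 74-77% → 78-79% | 62-64% → 66% | 47-49% → 51-52% |
| 3.52 | 66-72% → 77-79% | 52-56% → 62-64% | 39-44% → 49-52% |
| 4.94 | 57-67% → 76-78% | 47-53% → 62-65% | 34-40% → 47-50% |

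Within each mix, the gain is about 7-11 points at VAF hazard ratio 3.52, 9-18 at 4.94 and 2-5 at 2.0. At 1.0 the change is within 1 point here; a second simulation put the loss at 1-2 points. A cautious summary is therefore 1-5 points at 2.0, and nil or a loss of 1-2 points at 1.0.

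**Why power falls.** At VAF hazard ratio 3.52 and a true treatment hazard ratio of 0.65, the unadjusted model estimates 0.676-0.689 and the adjusted one 0.646-0.651. Schoenfeld with the attenuated values and the simulated deaths:
- sqrt(118.1/4) × |ln 0.689| − 1.96 = 0.06, power 53%.
- sqrt(119.8/4) × |ln 0.676| − 1.96 = 0.18, power 57%.

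Both are close to the simulated 52-56%.

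**The case against.** **A reader might infer that planned power is being given away.** The documents do not support that. They state no between-arm test, event count or power for OS, RFS or time to AML, and only CR is powered. The missing test is the more basic gap. The secondary objectives do set the combination against azacitidine alone, so a comparison is evidently intended, and naming the model closes both gaps.

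**A reader might infer a gain of about 15 points.** Splitting patients half and half into VAF-high and VAF-low and applying 3.52 between them (18 months' accrual, 30 months total, treatment hazard ratio 0.65) gives about 45% v 60%. But 3.52 contrasts above 40% with below 20% and leaves out 20-40%. The two-group split gives a log-hazard variance of 0.25 × (ln 3.52)² = 0.40. The three-group mixes give 0.26, 0.24 and 0.17. Follow-up does not explain the difference, since two groups at 33 months still give 45% v 62%.

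**A reader might stress chance imbalance.** With the same two groups, the SD of the imbalance is sqrt(2 × 0.25/77) = 0.081, so 10 points or more arises in about 21% of trials, and 3.52^0.10 = 1.13. This inherits the two-group assumption. The standard error of an unadjusted randomised comparison already allows for chance imbalance, so that comparison is valid, only less efficient.

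**The VAF evidence is limited.** P = 0.01 implies lower 95% limits near 1.35 (for 3.52) and 1.5 (for 4.94) by a Wald approximation, so the 2.0 row of the table is plausible. Section 2.2 does not say that these cohorts match this trial's treatment or risk groups. It gives no VAF result for RFS, time to AML or CR.

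**Availability is not assured.** Section 5.0 promises sequencing of TP53, not a reported VAF, and nothing requires local reports to state one. This stands, and the fix must deal with it.

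**Section 8.2.3 already adjusts for baseline predictors.** That analysis concerns transplant and does not name VAF. It does not replace an adjusted OS comparison.

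**Conclusion.** The point holds for OS. The plan leaves its most strongly documented prognostic variable for survival out of the OS analysis, although planned sequencing can supply it. If OS is compared between arms, adjustment would raise power by about 7-11 points at the protocol's lower VAF hazard ratio of 3.52, and by about 1-5 if the true value is nearer 2. The cost is at most 1-2 points if VAF has no effect. These sizes rest on the assumed treatment hazard ratio, accrual and VAF mix, and on placing the 20-40% group midway on the log-hazard scale.

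It does not show that the unadjusted comparison is invalid, that a stated power is wrong, or that RFS, time to AML or CR would gain likewise. This is an improvement that should be made to a secondary endpoint; the primary analysis is unaffected.

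**What to change.** Keep the age strata, the primary CMH test and N = 154. In Section 9.3.1:

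- Pre-specify for OS a Cox model stratified by age group and adjusted for baseline TP53 VAF. If a test is wanted, use a log-rank test stratified by age and VAF group; stratifying by age alone would not deliver the gain.
- Take VAF from the pre-treatment sample and fix its form in advance: continuous, or <20 / 20-40 / >40%.
- Make VAF a mandatory output of the central NGS, not an optional exploratory item.
- State rules for multiple TP53 mutations, for blood used in place of marrow, and for missing values (local report first, then a missing category).
- Keep the unadjusted Kaplan-Meier summary alongside, and describe the adjusted hazard ratio as conditional on VAF.
- Treat the same model for RFS and time to AML, and a logistic model for CR, as supportive only.

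The cost is analysis-plan wording, some programming and a firm reporting requirement for sequencing already planned. The drawback is a conditional hazard ratio that differs in meaning from the unadjusted one, which is why both should be shown.

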9.3.2 Exploratory Analyses

Descriptive statistics/results from the assays (DNA mutation panel, RNA expression profile, p53 IHC, TP53 VAF by NGS, PCR) will be written. Not all analyses listed may be performed.

9.3.3 Safety Analysis

Safety data will be summarized for the safety population. These data will include adverse events and laboratory parameters. Adverse event terms will be coded using the MedDRA[®], version 21.1 or higher. Adverse events will be summarized by body system, preferred term, severity, and relationship to treatment. Serious adverse events, deaths, and AEs leading to early discontinuation of study drug will be summarized. Laboratory parameters will be summarized by maximum NCI-CTCAE v5.0 severity grade and also by change from pre-treatment to scheduled time points using descriptive statistics. Laboratory parameter listings will include the normal ranges for each parameter. Each value will be classified as falling above, below, or within the normal range.

Data summaries will include only treatment-emergent adverse events (TEAEs), defined as events occurring at the start of infusion on Day 1, Cycle 1 up to and including 30 days after last dose.

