2.8 Potential Risks and Benefits

2.8.1 Potential Risks

Potential risks identified with APR-246 include transient CNS-related adverse events, bone marrow suppression, QTc prolongation, glucuronidation of acetaminophen.

CNS adverse events:

Non-clinical data have shown APR-246 induced CNS adverse effects at high concentration levels in mice and dogs. The effects were transient and occurred during or in direct connection with dosing (related to high C_{max}). They are fully reversible, usually mild and non-severe, and may be managed by supportive medication (see Section 6.2.2) and/or dose reductions. However, cases with severe intensity have occurred, including events defined as a dose-limiting toxicity. Please consult with the Medical Monitor if you are unfamiliar with these events.

Bone marrow suppression:

No hematological toxicity was detected in nonclinical and clinical studies nor when APR/246 has been dosed alone, but when combined with carboplatin and pegylated liposomal doxorubicin in the study in HGSOc performed under IND 124841, there have been events of agranulocytosis (×1), anemia (×3), febrile neutropenia (×6), leucopenia (×1) and thrombocytopenia (×8). To date there have been no clinical or non-clinical data to support or rule out a contribution from APR-246 to chemotherapy induced bone marrow suppression.

REDACTED

Glucuronidation of Acetaminophen:

Based on co-administration studies in mice, it cannot be excluded that APR-246 may have a negative influence on the glucuronidation of acetaminophen, and therefore potentially potentiating hepatotoxicity after an over-dose of acetaminophen. No hepatotoxicity caused by acetaminophen has been identified in the ongoing clinical studies.

The Investigator's Brochure (IB) may be updated during the course of this study with additional risks and benefits. Please see the current IB for further details about the potential risks and benefits associated with this study.

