- i. **Bone marrow aspirate sample and biopsy core is collected at baseline and when bone marrow is sampled for disease assessment. If no aspirate is available, then peripheral blood is acceptable. Bone marrow assessment completed within 28 days of signing consent will be accepted to fulfill screening requirement, as long as it has been completed following the last MDS treatment (excluding ESAs (erythropoietic stimulating agent)).**
- j. Hematology including hemoglobin, hematocrit, MCV, platelet count, blasts, WBC and WBC differentials weekly. **The peripheral blood sample collected on Day 1 of each cycle starting at Cycle 2 will be for disease assessment, if bone marrow aspirate is not available (see footnote r).** For patients with documented CR at disease assessment following Cycle 2, hematology and blood chemistry assessments will be required for D1 of each subsequent cycle and more frequently per the discretion of the treating physician. Otherwise performed weekly until CR.

- k. Blood chemistry including sodium, potassium, BUN, glucose, ALT/AST, alkaline phosphatase, total protein, total bilirubin, albumin, creatinine, calcium, chloride and magnesium weekly. At screening, the creatinine clearance may be calculated from the serum creatinine. A 24-hour urine for Creatinine Clearance may be performed at investigator's discretion. For patients with documented CR at disease assessment following Cycle 2, hematology and blood chemistry assessments will be required for D1 of each subsequent cycle and more frequently per the discretion of the treating physician. Otherwise perform weekly until CR.
- l. Pregnancy test; for women of childbearing potential, a negative pregnancy test (urine or serum) must be documented between Screening and first day of treatment on study. Must be documented prior to 1st dose of treatment on study.
- m. Standard 12-lead ECGs to be performed in triplicate at baseline/screening, on Days 1 - 4 of Cycle 1 (experimental arm only) and on Days 1 of each subsequent cycle (experimental arm only) with patient in a semi-recumbent position. Please consult Table 10 for ECG collection schedule.
- n. Please consult section 8.3, Table 9 for PK collection schedule.

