8.1.1 Safety Analysis

Safety data including AEs, vital signs, laboratory data, ECG, and physical exam will be tabulated for the safety population. Adverse events will be tabulated by body system, preferred term, severity, and relationship to treatments. The tabulation of laboratory parameters will include the normal ranges for each parameter. Each value will be classified as falling above, below, or within the normal range. Laboratory parameters will also be tabulated by maximum NCI-CTCAE severity grade.

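### For blood counts, the maximum-grade laboratory table ignores baseline grade, so cytopenia present at entry dilutes the between-arm difference at Grade 3-4; add baseline-to-worst shift tables

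*Combined protocol and SAP*

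**What the plan says.** Section 9.3.3 gives two laboratory summaries, one by worst grade and one that refers to baseline: "Laboratory parameters will be summarized by maximum NCI-CTCAE v5.0 severity grade and also by change from pre-treatment to scheduled time points". The second is descriptive only. Each value is also classed as above, below or within the normal range. Section 8.1.1 has the grade table alone ("Laboratory parameters will also be tabulated by maximum NCI-CTCAE severity grade"), and so does the Safety Analyses part of the synopsis. None of the three crosses maximum grade with baseline grade, requires worsening, or says that the maximum is taken after the first dose.

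Adverse event summaries are limited to treatment-emergent events, "defined as events occurring at the start of infusion on Day 1, Cycle 1 up to and including 30 days after last dose". That definition rests on timing and has no worsening clause.

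Section 2.8.1 leaves a safety question open. It says there are so far no clinical or non-clinical data "to support or rule out a contribution from APR-246 to chemotherapy induced bone marrow suppression".

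**The concern.** Section 2.1 describes MDS as a disease of blood cytopenias. Section 5.1 sets renal and hepatic entry limits but none for ANC, platelets or haemoglobin. The footnote to the haematological part of Table 6 restricts those rows to patients with normal baseline ANC and platelets, so the protocol itself expects abnormal counts at entry. The maximum-grade table makes no such distinction: a patient who enters at Grade 4 neutropenia and stays there looks the same as one who falls from normal to Grade 4.

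What is at stake is a question that this trial is well placed to inform. Section 2.6.1 reports myelosuppression as the most common drug-related event with the same combination in the earlier Phase Ib/II study, and Section 2.8.1 leaves the contribution of APR-246 unresolved. Here there is a randomized azacitidine-alone arm, yet the grade table would understate any added toxicity at Grade 3-4.

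**Working it through.** **The plan's own figure.** The plan gives no figure for the laboratory tables. Its only design calculation is for CR (Section 9.1): 25% v 50%, two-sided alpha 0.05, 90% power. A two-proportion formula with pooled variance and no continuity correction gives 77 per arm, 154 in total, with power 90.1%. It reproduces and is unaffected by this point.

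**Inputs for the dilution.**
- Arm size: 77 (Section 9.1).
- b, the share at Grade 3-4 at baseline: not in the documents. Assumed 30%, 50% or 70%, equal in expectation across arms by randomization.
- e and c, new Grade 3-4 among the remaining patients in the experimental and control arms: not in the documents. Assumed 60% and 40%.
- The maximum is taken over a period in which a patient who enters at Grade 3-4 is recorded at that grade at least once.

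**Formula.** The maximum-grade table shows b + (1-b)e against b + (1-b)c. The difference is (1-b)(e-c).

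| b | Experimental | Control | Difference shown | Difference among patients at risk |
|---|---|---|---|---|
| 30% | 0.30 + 0.70 × 0.60 = 72% | 0.30 + 0.70 × 0.40 = 58% | 14 points | 20 points |
| 50% | 0.50 + 0.50 × 0.60 = 80% | 0.50 + 0.50 × 0.40 = 70% | 10 points | 20 points |
| 70% | 0.70 + 0.30 × 0.60 = 88% | 0.70 + 0.30 × 0.40 = 82% | 6 points | 20 points |

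With assumed rates of 45% v 30%, a true 15-point difference falls to 12, 9 and 6 points at b = 20%, 40% and 60%. The direction holds for any b above zero; only the size depends on the assumptions.

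**Does restricting the denominator lose more than it gains?** As a yardstick only, since no safety test is planned, I computed the exact power of a pooled two-proportion test at two-sided 0.05 for the 60% v 40% case. All 77 per arm in the maximum-grade table are compared with the at-risk patients, about 77(1-b) per arm:
- b = 30%: 45% v 53% (54 per arm at risk)
- b = 50%: 30% v 42% (38 per arm)
- b = 70%: 18% v 29% (23 per arm)

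The at-risk comparison does better despite the smaller denominator.

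**Do the other planned summaries fill the gap?**
- *Change from pre-treatment* describes values at scheduled visits and does not count patients who worsened. Appendix II requires haemoglobin of at least 11 g/dL, platelets of at least 100 × 10⁹/L and neutrophils of at least 1.0 × 10⁹/L for CR, and the design assumes CR in 50% v 25%. Rising counts in responders can therefore offset falls in others, more so in the experimental arm if the drug works.
- *Normal-range classification* adds little: a cytopenic patient can be below range both before and after.
- *Treatment-emergent event tables* do capture Grade 3-4 laboratory abnormalities, because Section 8.1.2.1 counts abnormal laboratory values as adverse events and exempts from recording only Grade 1-2 abnormalities that need no intervention. With timing as the only criterion, however, the text does not settle how to treat a cytopenia that began before treatment and then worsened, or one that simply persisted.

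**The case against.** The strongest reply is that baseline is not ignored. The same sentence in Section 9.3.3 plans change from pre-treatment, and its descriptive statistics may include minima and quartiles as well as means. New Grade 3-4 cytopenias are recorded as adverse events, whose occurrence Section 8.1.2.1 ties to changes in laboratory results, and are summarized by severity and relationship. These routes are real and reduce the concern. They do not give a clean count of patients who worsened from a known baseline grade.

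Several stronger readings are tempting, and the documents do not support them:
- A reader might infer that all laboratory toxicity is affected, chemistry included. In Table 6 the creatinine grades, and the AST/ALT grades for patients with abnormal baseline values, already refer to baseline. The point belongs to the blood counts.
- A reader might infer that the table will be near its ceiling in both arms. That needs a high b, which the documents do not give; at b = 30% it reads 72% v 58%.
- A reader might cite the reduced sampling after a documented CR, when "hematology and blood chemistry assessments will be required for D1 of each subsequent cycle", as a reason for shift tables. A nadir that is not sampled is missing from a shift table too. Counts are otherwise weekly until CR, so early worsening is captured either way.
- A reader might take the power figures as a failure of the design. No safety hypothesis test is planned, and the at-risk comparison itself reaches only 29% to 53%. Neither table would settle the marrow question.

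Worsening from Grade 3 to Grade 4 stays visible in the planned table if each maximum grade is shown separately. Section 9.3.1 refers to a Statistical Analysis Plan, but only for subgroups.

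**Conclusion.** The point holds for ANC, platelets and haemoglobin. At Grade 3-4 the maximum-grade table attenuates any between-arm difference by the factor (1-b). Under the assumed 60% v 40%, 20 points become 14, 10 or 6 at b = 30%, 50% or 70%; b and both onset rates are assumptions. Randomization makes this a loss of contrast rather than bias toward an arm. The other planned summaries offset it in part. It is a low-severity improvement to reporting, with no effect on the sample size or the primary analysis.

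**What to change.** In Section 9.3.3, and to match in Section 8.1.1 and the synopsis:
1. Keep the maximum-grade table.
2. Add, by arm, a shift table from baseline grade to worst grade after the first dose for ANC, platelets and haemoglobin, with every grade shown separately so that Grade 3 to 4 worsening can be seen.
3. Add, by arm, the proportion worsening to Grade 3 or higher among patients below Grade 3 at baseline, with that denominator stated.
4. Add *or worsening from baseline* to the treatment-emergent definition.

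Baseline and on-treatment counts are already collected (Section 7.2.1 and the hematology footnote to the Schedule of Study Evaluations). The cost is a little more programming and smaller denominators for the at-risk proportion: about 54, 38 or 23 per arm at b = 30%, 50% or 70%.
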